Appendix A

1 History of heart valve disorders (ie, prosthetic valve or hemodynamically relevant valve disease)
	
Measured anytime prior to and including day of drug initiation in any diagnosis position and inpatient care setting 394.x (diseases of mitral valve), 395.x (diseases of aortic valve), 396.x (diseases of mitral and aortic valve) 397.x (diseases of other endocardial structures), 398.9x (other and unspecified rheumatic heart diseases) V42.2 (heart valve replaced by transplant), V43.3 (heart valve replaced by a mechanical device/prosthesis) -OR- ICD-9 procedure code 35.1x (open heart valvuloplasty without replacement), 35.2x (replacement of heart valve) -OR- one of the following CPT codes: 33660-33665 (atrioventricular valve repair) 33400-33403 (aortic valve valvuloplasty) 33405 (Replacement, aortic valve, with cardiopulmonary bypass; with prosthetic valve other than homograft or stentless valve) 33420-33430 (mitral valve repair/valvuloplasty/replacement) 33460 (valvectomy, tricuspid valve, with cardiopulmonary bypass) 33463-33468 (tricuspid valve repair/valvuloplasty/replacement) 33475 (replacement, pulmonary valve) 33496 (prosthetic valve dysfunction repair) 025.1 (implantation of catheter-delivered prosthetic aortic heart valve; open thoracic approach) 0258T (transthoracic cardiac exposure for catheter-delivered aortic valve replacement; without cardiopulmonary bypass) 0259T (transthoracic cardiac exposure for catheter-delivered aortic valve replacement; with cardiopulmonary bypass) 0262T (implantation of catheter-delivered prosthetic pulmonary valve, endovascular approach)
	

Severe, disabling stroke within the previous 6 months 2 or Any stroke within the previous 14 days
	
1) Disabling stroke effects Measured 180 days prior to and including day of drug initiation in any diagnosis position and inpatient or outpatient care setting ICD-9 diagnosis: 438.xx (Late effects of cerebrovascular disease) ICD-10 diagnosis: I69 (Sequelae of cerebrovascular disease (hemiplegia etc)) ICD10 diagnosis: Z73.6 (Limitation of activities due to disability) -OR- 2) Any stroke: Measured 14 days prior to and including day of drug initiation in primary diagnosis position and inpatient care setting ICD-9 diagnosis: 430.xx, 431.xx, 433.xx, 434.xx, 436.xx
	

3 Conditions associated with an increased risk of bleeding:
 
3a • Major surgery in the previous month
	
Measured 30 days prior to and including day of drug initiation in any procedure position and inpatient or outpatient care setting. ICD-9 procedure codes: Major surgery selected from codes range 34.x- 84.x 30-34 Operations On The Respiratory System 35-39 Operations On The Cardiovascular System 40-41 Operations On The Hemic And Lymphatic System 42-54 Operations On The Digestive System 55-59 Operations On The Urinary System 60-64 Operations On The Male Genital Organs 65-71 Operations On The Female Genital Organs 72-75 Obstetrical Procedures 76-84 Operations On The Musculoskeletal System
	

3b • Planned surgery or intervention in the next 3 m
	
N/A
	

3c • History of intracranial, intraocular, spinal, retroperitoneal or atraumatic intra-articular bleeding
	
Measured anytime prior to and including day of drug initiation in any diagnosis position and inpatient care setting Intracranial hemorrhage: ICD-9: 430.x, 431.x, 432.x Intracocular hemorrhage: 379.23 vitreous hemorrhage, H43.1x 362.81 retinal hemorrhage H35.6x
	

Appendix A

		Measured 365 days prior to and including day of drug initiation in any diagnosis position and inpatient or outpatient care setting: ICD-9 diagnosis: 578.x Gastrointestinal hemorrhage ICD-10 diagnosis: K92.2: Gastrointestinal hemorrhage, unspecified acute hemorrhagic gastritis (K29.01) peptic ulcer with hemorrhage (K25.x - excluding K25.9 - K26.x - excluding K26.9 - K27.x-K28.x) gastritis and duodenitis with hemorrhage (K29.x) diverticular disease with hemorrhage (K57.x) angiomyolipoma of stomach with hemorrhage (K31.811) CPT/HCPGS: 0W3P8Z - (ICD10) Control Bleeding in Gastrointestinal Tract, Via Natural or Artificial Opening Endoscopic 43255 - (HCPGS) Esophagogastroduodenoscopy, flexible, transoral; with control of bleeding, any method / Upper gastrointestinal endoscopy including esophagus, stomach, and either the duodenum and/or jejunum as appropriate; with control of bleeding, any method 44.43 - (ICD9) ENDOSCOPIC CONTROL OF GASTRIC OR DUODENAL BLEEDING	
	3e • Symptomatic or endoscopically documented gastroduodenal ulcer disease in the previous 30 days	Measured 30 days prior to and including day of drug initiation in any diagnosis position and inpatient or outpatient care setting: ICD-9 diagnosis: Disease of esophagus: 530.1x-530.4x, 530.8x, 530.9x Gastric ulcer: 531.x Duodenal ulcer: 532.x Peptic ulcer: 533.x Acute gastritis: 535.0x Other specified gastritis: 535.4x Unspecified gastritis and gastroduodenitis: 535.5x Duodenitis: 535.6x ICD-10 diagnosis: Peptic ulcer, site unspecified K27.x K25.9 - Gastric ulcer, unspecified as acute or chronic, without hemorrhage or perforation K26.9 Duodenal ulcer, unspecified as acute or chronic, without hemorrhage or perforation	
	3f • Hemorrhagic disorder or bleeding diathesis	Measured 180 days prior to and including day of drug initiation in any diagnosis position and inpatient or outpatient care setting Bleeding diathesis: ICD-9 diagnosis: 286.x Coagulation defects 287.x Purpura and other hemorrhagic conditions ICD-10 diagnosis: D65.x Disseminated intravascular coagulation [defibrination syndrome] D66.x Hereditary factor VIII deficiency D67.x Hereditary factor IX deficiency D68.x Other coagulation defects D69.x Purpura and other hemorrhagic conditions	
3g	• Need for anticoagulant treatment of disorders other than Atrial fibrillation	N/A	
3h	• Fibrinolytic agents within 48 h of study entry	We will censor the patients upon initiating these drugs after cohort entry: Fibrinolytic agent: Alteplase, reteplase, tenecteplase, streptokinase, urokinase	
3i	• Uncontrolled hypertension (systolic blood pressure >180 mm Hg and/ or diastolic blood pressure >100 mm Hg)	Measured 180 days prior to and including day of drug initiation in any diagnosis position and inpatient or outpatient care setting Malignant hypertension: ICD-9 diagnosis: 401.0x (no ICD-10) Hypertensive urgency/ Hypertensive crisis: ICD-10 diagnosis: I16.x (no ICD-9)	
3j	• Recent malignancy or radiation therapy (≤6 m) and not expected to survive 3 y	N/A	
4	• Contraindication to warfarin treatment	N/A	
5	• Reversible causes of atrial fibrillation (eg, cardiac surgery, pulmonary embolism, untreated hyperthyroidism).	N/A	
6	• Plan to perform a pulmonary vein ablation or surgery for cure of the AF	N/A	
7	• Severe renal impairment (estimated creatinine clearance ≤30 mL/min)	Measured 180 days prior to and including day of drug initiation in any diagnosis position and inpatient or outpatient care setting CKD stage 4/5/ESRD ICD-9 diagnosis: 585.4x, 585.5x, 585.6x ICD-10 diagnosis: N18.4x, N18.5x, N18.6x Dialysis/ Renal transplant Codes are in the sheet "Dialysis and Renal Transplant"	

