5.2.2 Specify inclusion/exclusion criteria for cohort entry and define the index date

Inclusion and exclusion criteria were adapted from the trial as closely as possible. Definitions for all inclusion/exclusion are provided in **Appendix A** and are summarized in the flowcharts below.

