6.3.1 Outcome variables

Primary Effectiveness outcomes of interest: (definitions provided in **Appendix A**):

- **Primary Outcome:** Stroke (hemorrhagic, ischemic) and systemic embolism
- **Secondary outcomes:** Individual components
 - Hospital admission for stroke (principal diagnosis position)
 - Hospital admission for systemic embolism (principal diagnosis position)

Control outcomes of interest (control outcomes only serve to assess aspects of study validity but are not further interpreted):

1. Major bleeding

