6.3.2 Study follow-up

Both as-treated (AT) and intention-to-treat (ITT) analyses will be conducted with treatment defined as the index drug on the day of cohort entry. Because adherence in the real-world databases is expected to be much worse than in the trial, the AT analysis is the **primary** analysis, as it targets the relative hazard of outcomes on treatment.

For the AT analyses, the follow-up will start the day after initiation of apixaban and comparator and will continue until the earliest date of the following events:

- The first occurrence of the outcome of interest, unless otherwise specified for selected outcomes,
- The date of end of continuous registration in the database,
- End of the study period,
- Measured death event occurs,

- Nursing home admission
 - Nursing home admissions are considered a censoring event because the data sources utilized typically provide little to no data on a patient, particularly on drug utilization, after admission. We will utilize this as an exclusion reason for cohorts for the same reason.
- The date of drug discontinuation, defined as the date of the last continuous treatment episode of the index drug (dabigatran and comparator) plus a defined grace period (i.e., 10 days after the end of the last prescription's days' supply in main analyses).
- The date of augmentation or switching from exposure to comparator or vice versa or augmentation/switching to any other NOAC (e.g. switching from dabigatran or warfarin to apixaban would be a censoring event);
 - A dosage change on the index treatment does not fulfill this criterion
 - An added treatment that is not part of the exposure or comparator group does not fulfill this criterion
- Dispensing of a fibrinolytic agent

For the intention-to-treat (ITT) analyses, the censoring based on the augmentation/switching and treatment discontinuation will be replaced with a maximum allowed follow-up time of 365 days.

7. Initial Feasibility Analysis

Action report name:

For dabigatran vs. warfarin

Optum- <https://bwh-dope.aetion.com/projects/details/707/results/59579/result/0>

Marketscan- <https://bwh-dope.aetion.com/projects/details/708/results/59601/result/0>

Medicare- <https://bwh-dope.aetion.com/projects/details/709/results/59602/result/0>

Date conducted: 10/5/20 (Medicare 10/6/20)

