After review of initial feasibility and power analyses, complete creation of the remaining covariates (see Table 1 below for list of covariates). Again, using the dummy outcome of a 90-day gap in database enrollment, complete a 1:1 PS-matched analysis. The PS should include the complete list of covariates (excluding laboratory values, which are missing in some patients).

- Provide plot of PS distributions stratified by treatment group.

Note- Please refer to **Appendix B**.

- Report covariate balance after matching.

Note- For Table 1, please refer to **Appendix B**.

- Report reasons for censoring by treatment group.

	Overall	Referent	Exposure
Dummy Outcome	0 (0.00%)	0 (0.00%)	0 (0.00%)
Death	657 (0.84%)	369 (0.94%)	288 (0.74%)
Start of an additional exposure	2,760 (3.53%)	1,189 (3.04%)	1,571 (4.02%)
End of index exposure	62,039 (79.39%)	31,190 (79.83%)	30,849 (78.96%)
Specified date reached (Dec 17/Dec 18/Dec 19)	2,483 (3.18%)	1,281 (3.28%)	1,202 (3.08%)
End of patient enrollment	4,128 (5.28%)	1,938 (4.96%)	2,190 (5.61%)
Switch to other NOACs (for censoring) + nursing home admission	6,073 (7.77%)	3,103 (7.94%)	2,970 (7.60%)

- Report follow-up time by treatment group.

Median Follow-Up Time (Days) [IQR]			
Patient Group	Optum	Truven	Medicare
Overall Patient Population	98 [38-191]	98 [38-193]	98 [38-202]

Referent	98 [43-192]	98 [43-178]	98 [42-196]
Exposure	98 [38-190]	98 [38-220]	98 [38-211]

- Report overall risk of the primary outcome.

	Optum	MarketScan	Medicare	Pooled
Risk per 1,000 patients	4.57	5.20	6.04	5.64

10. Final Power Assessment

Date conducted:

- Re-calculate power in the appropriate excel table, using the revised number of matched patients from the PS-match in Section 9. All other parameters in the table should be the same as in Section 8. If the study is to be implemented in more than one database, copy and paste excel sheet to report power for each database separately and for the pooled analysis that uses data from all databases together. Power calculations are based on the formulas from Chow et al. (2008).
 - For dabigatran 150mg vs. warfarin
 - Pooled

Superiority Analysis		Non-inferiority Analysis	
Number of patients matched	78,140	Number of patients matched	78,140
Reference	39,070	Reference	39,070
Exposed	39,070	Exposed	39,070
Risk per 1,000 patients	5.64	Risk per 1,000 patients	5.64
Desired HR from RCT	0.66	Assumed HR from RCT	1
Alpha (2-sided)	0.05	Alpha (2-sided)	0.05
		Non-inferiority margin	1.46

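### Trial exclusion 3h (fibrinolytic within 48 hours of entry) is applied as censoring after entry, in AT and ITT, instead of at baseline, so a primary event could be censored by its own treatment

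*Combined protocol and SAP*

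**What the plan says.** - **The aim.** Section 5.2.2: "Inclusion and exclusion criteria were adapted from the trial as closely as possible".
- **The trial criterion.** Appendix A lists 3h under the exclusion criteria, in the group of conditions that raise bleeding risk: "Fibrinolytic agents within 48 h of study entry".
- **Its implementation.** The Appendix A cell for 3h names five agents and gives no look-back window. It reads: "We will censor the patients upon initiating these drugs after cohort entry". The Section 5.3 flowchart goes from 3f straight to 3i.
- **As-treated follow-up.** Section 6.3.2 starts follow-up the day after initiation and says it "will continue until the earliest date of the following events". The list contains both the first outcome and "Dispensing of a fibrinolytic agent".
- **ITT follow-up.** The same section says "the censoring based on the augmentation/switching and treatment discontinuation will be replaced with a maximum allowed follow-up time of 365 days". No other censoring item is mentioned as changed.
- **The outcome.** Section 6.3.1 defines the components as hospital admissions, and Appendix A defines them as inpatient primary-position diagnoses. Neither says which date of the stay is the event date, and no section says which item wins when two share a date.

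**The concern.** Two things follow from moving 3h from before entry to after it.

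First, a patient given a fibrinolytic in the 48 hours before or on the index day meets neither rule: 3h is not applied at baseline, and the censoring looks only at what comes after entry. Criterion 3h is not marked as unmeasurable. The plan names the drugs and intends to detect them.

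Second, the censoring trigger can be a consequence of the outcome. Fibrinolytics can be given to treat ischemic stroke or arterial embolism; this is general clinical knowledge, not a statement in the documents, and other indications exist. If the drug claim is dated ahead of the recorded event, the patient leaves as censored and a true event is not counted. Such censoring is informative. Because the rule remains in ITT as worded, comparing AT with ITT would not reveal it.

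At stake is a possible bias in the hazard ratio if such losses differ between arms. Precision is not the issue.

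**Working it through.** **1. How the group-3 criteria are mapped (Appendix A against the Section 5.3 flowchart).**

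| Handling | Criteria | Count |
|---|---|---|
| Flowchart row | 3a, 3c, 3d, 3e, 3f, 3i | 6 |
| N/A | 3b, 3g, 3j | 3 |
| Censoring after entry | 3h | 1 |

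6 + 3 + 1 = 10. Only 3h becomes a post-entry rule, and no reason is given.

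**2. What the earliest-date rule does to a primary event treated with a fibrinolytic.**

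| Order of recorded dates | Result under Section 6.3.2 |
|---|---|
| Outcome first | Event counted; the rule has no effect |
| Same date | Undefined; lost if censoring takes precedence |
| Fibrinolytic first | Censored; event not counted |

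If events carry the admission date, mainly the middle row is exposed. If they carry a discharge or later claim date, the last row opens up. The documents do not say which applies.

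**3. What the Section 9 run shows.** The censoring rows, with 0 dummy outcomes, sum as follows:

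- Overall: 657 + 2,760 + 62,039 + 2,483 + 4,128 + 6,073 = 78,140
- Referent: 369 + 1,189 + 31,190 + 1,281 + 1,938 + 3,103 = 39,070
- Exposure: 288 + 1,571 + 30,849 + 1,202 + 2,190 + 2,970 = 39,070

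Every matched patient is accounted for without a fibrinolytic row. The instruction for that run was "using the dummy outcome of a 90-day gap in database enrollment, complete a 1:1 PS-matched analysis", so a stroke did not end follow-up and could not pre-empt the rule. Fibrinolytic censoring was therefore inert, merged into another row (the last row already combines two reasons), or not implemented. The table does not tell these apart.

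**4. Power.** Inputs from Section 10, pooled: 78,140 patients, 5.64 events per 1,000, HR 0.66, margin 1.46, two-sided alpha 0.05.

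Events D = 78,140 × 5.64 / 1,000 = 440.7. Power = Φ(|ln(effect)| × √D / 2 − 1.96).

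- Superiority: 0.4155 × 20.993 / 2 − 1.96 = 2.40, giving 0.992 (plan: 0.9918)
- Non-inferiority: 0.3784 × 20.993 / 2 − 1.96 = 2.01, giving 0.978 (plan: 0.9779)

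The plan's figures reproduce. Now remove an assumed share f of events. The documents give no value for f; these are stress values.

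| f | Events | Superiority | Non-inferiority |
|---|---|---|---|
| 2% | 431.9 | 0.991 | 0.976 |
| 5% | 418.7 | 0.989 | 0.972 |
| 10% | 396.6 | 0.985 | 0.965 |
| 20% | 352.6 | 0.974 | 0.944 |

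**5. Hazard ratio.** Approximately, observed HR = true HR × (1 − f in exposed) / (1 − f in referent). Equal loss cancels. For an assumed 10% against 5%:

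- True HR 0.66: 0.66 × 0.90 / 0.95 = 0.625 if more is lost in the exposed arm; 0.66 × 0.95 / 0.90 = 0.697 if more is lost in the referent arm
- True HR 1.00: 0.947 or 1.056

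These show sensitivity only. Nothing in the documents indicates the loss in either arm.

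**The case against.** The strongest reply is that no harm is shown. The only empirical evidence, the Section 9 table, has no fibrinolytic row. The mechanism needs in-hospital drug use to be captured, yet Section 6.3.2 speaks of dispensing, and the 3h cell gives drug names only, with no procedure codes. An outcome dated first still counts. All of this stands, and it is why the point is minor.

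The absence of a tie rule is also not special to fibrinolytics: a stroke and a death on the same day are equally unresolved. That stands too. It is missing detail across the whole list, as is the difference between dispensing and initiating in the two descriptions of the trigger.

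The rule has a plausible purpose. Criterion 3h is a bleeding-risk criterion, the primary outcome includes hemorrhagic stroke, and major bleeding is the control outcome. Censoring at a fibrinolytic keeps later bleeds from being attributed to the anticoagulant. A reader might infer that the rule can only lose events and should be deleted outright. The documents do not support that: deletion would count hemorrhagic strokes that follow fibrinolytics given for other reasons, so it trades one possible bias for another.

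On the baseline part, the adaptation is openly stated in Appendix A, and the trial wording does not say that the 48 hours precede entry. But a baseline exclusion can use only what is known by the index date, so a look-back is the natural reading. Exclusion 2b already removes inpatient primary-position strokes in the 14 days through the index day. It covers the gap in part, since it depends on a stroke diagnosis and not on the drug.

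**Conclusion.** The concern holds as a minor one. The text establishes that 3h is not applied at baseline, that it is replaced by censoring after entry which on the wording runs in both AT and ITT, and that this censoring shares an earliest-date rule with the outcome. A primary event whose fibrinolytic claim is dated earlier would be censored under the rule as written.

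That a fibrinolytic may treat the outcome is outside knowledge. Whether any such claim is captured and dated ahead of the event is unknown. Frequency, direction and size therefore cannot be stated and may be nil. A reader might infer that events are being lost or that the hazard ratio is biased; the documents show neither. Nor is power materially affected: even the assumed 20% loss leaves it at 0.944 or higher in the pooled analysis.

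What remains is a departure from the trial criterion without a stated reason, and a possible source of informative censoring that ITT does not check and that is cheap to close.

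**What to change.** 1. Apply 3h as a baseline exclusion using the trial's 48-hour window, expressed in days up to and including the index day as in the other Appendix A rows, with its own flowchart row.
2. If fibrinolytic censoring is kept, add one sentence for both AT and ITT: a stroke or systemic embolism dated on the fibrinolytic date, or belonging to the same episode or hospital stay, counts as an event. State which date of the stay is the event date, and use one term for the trigger in Section 6.3.2 and Appendix A.
3. Report the primary outcome without fibrinolytic censoring as a sensitivity analysis, not as the required primary change, because of the later hemorrhagic strokes it would bring in.
4. Say whether the rule was active in the Section 9 run, and give fibrinolytic censoring its own row by arm in Table 3 (Section 14.3).

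Cost: one attrition step that removes a small, unknown number of patients, a few lines of wording, and one extra analysis. The date in Section 13 is blank in this version, which does not show whether comparative analyses have since been run. If they have, items 1 and 2 can be reported as sensitivity analyses as well.

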Excluded based on Exclusion 10 & 11 - Pregnancy & Anemia and Thrombocytopenia	-191	25,673	-1,229	82,993	-2,798	163,724
Excluded based on Exclusion 14 - Alcohol abuse or dependence	-28	25,645	-103	82,890	-138	163,586
Excluded based on Exclusion 14 - Drug abuse or dependence	-22	25,623	-47	82,843	-111	163,475
Excluded based on Exclusion 14 - CCI (180 days)	-7	25,616	-47	82,796	-1,939	161,536
Final cohort		25,616		82,796		161,536

* Medicare database includes all patients using a novel oral anticoagulant and a subset of patients using warfarin during 2011-2017.

6. Variables

6.1 Exposure-related variables:

Study drug:

The study exposure of interest is initiation of dabigatran. Initiation will be defined by no use of dabigatran or a comparator in the prior 6 months before treatment initiation (washout period).

Comparator agents-

- Initiators of dabigatran (150mg) will be compared to initiators of-
 - Warfarin

6.2 Covariates:

- Age
- Sex
- Combined Comorbidity Index (CCI), measured over the baseline covariate assessment period, defined as 180 days prior to and including index date

Covariates listed above represent only a small subset of covariates that will ultimately be controlled for in the design and analysis. We use the covariates above only for initial feasibility analyses to judge whether there is likely to be sufficient overlap between treatment groups to proceed with the study. Remaining covariates are defined only after the study has passed the initial feasibility analysis and the initial power assessment and are listed in Table 1 (**Appendix B**).

6.3 Outcome variables and study follow-up:

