14	Patients considered unreliable by the investigator or have a life expectancy less than the expected duration of the trial because of concomitant disease, or has any condition which in the opinion of the investigator, would not allow safe participation in the study (eg, drug addiction, alcohol abuse)	
Measured 180 days prior to and including day of drug initiation in any diagnosis position and inpatient or outpatient care setting
 
CCI >=10 (life expectancy less than the expected duration of the trial) -OR- Alcohol abuse or dependence ICD-9 diagnosis: 291.xx, 303.xx, 305.0x, 571.0x, 571.1x, 571.2x, 571.3x, 357.5x, 425.5x, E860.0x (CMS has not released mapping for new ICD10 for this code), V11.3x ICD-10 diagnosis: F10.x, K70.x, G62.1, I42.6, 099.31x Drug abuse or dependence 292.xx, 304.xx, 305.2x-305.9x, 648.3x 965.0x, 967.xx, 969.4x-969.6x, 969.72-969.79, 970.81 ICD-10 diagnosis: F11.x, F12.x, F13.x, F14.x, F15.x, F16.x, F18.x, F19.x, G62.0, 099.32x
	
15	Any known hypersensitivity to galactose if the warfarin used contains galactose.	N/A	

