Appendix B

Lab result number- Serum sodium mean (only >90 and <190 included)	579	654	92	122	N/A	N/A	671	776
...mean (sd)	140.03 (2.74)	140.11 (3.01)	-0.03	139.22 (2.71)	139.28 (2.99)	-0.02	N/A	139.92 (2.74)
...median [IQR]	140.00 [138.50, 142.00]	140.00 [139.00, 142.00]	0.00	139.80 [138.00, 141.00]	139.83 [137.50, 141.00]	-0.01	N/A	139.97 (2.74)
...Missing: n (%)	2,211 (79.2%)	2,136 (76.6%)	0.06	13,868 (99.3%)	13,838 (99.1%)	0.02	N/A	16,079 (96.0%)
Lab result number- Albumin mean (only >0 and <=10 included)	530	601	72	102	N/A	N/A	602	703
...mean (sd)	4.17 (0.31)	4.19 (0.31)	-0.06	4.10 (0.58)	4.03 (0.49)	0.13	N/A	4.16 (0.35)
...median [IQR]	4.20 [4.00, 4.40]	4.20 [4.00, 4.40]	0.00	4.20 [3.90, 4.40]	4.10 [3.89, 4.30]	0.19	N/A	4.20 (0.35)
...Missing: n (%)	2,260 (81.0%)	2,189 (78.5%)	0.06	13,888 (99.5%)	13,858 (99.3%)	0.03	N/A	16,148 (96.4%)
Lab result number- Glucose (fasting or random) mean (only 10-100 included)	576	645	91	111	N/A	N/A	667	756
...mean (sd)	110.45 (33.39)	111.79 (39.37)	-0.04	139.94 (58.19)	128.83 (44.07)	0.22	N/A	114.47 (37.74)
...median [IQR]	101.00 [91.00, 118.88]	100.50 [91.00, 117.00]	0.01	122.00 [96.75, 162.50]	117.00 [102.00, 140.00]	0.10	N/A	103.87 (37.74)
...Missing: n (%)	2,214 (79.4%)	2,145 (76.9%)	0.06	13,869 (99.3%)	13,849 (99.2%)	0.01	N/A	16,083 (96.0%)
Lab result number- Potassium mean (only 1-7 included)	603	679	108	143	N/A	N/A	711	822
...mean (sd)	4.35 (0.43)	4.38 (0.44)	-0.07	4.35 (0.37)	4.34 (0.38)	0.03	N/A	4.35 (0.42)
...median [IQR]	4.30 [4.10, 4.60]	4.40 [4.10, 4.65]	-0.23	4.30 [4.10, 4.60]	4.36 [4.10, 4.60]	-0.16	N/A	4.30 (0.42)
...Missing: n (%)	2,187 (78.4%)	2,111 (75.7%)	0.06	13,852 (99.2%)	13,817 (99.0%)	0.02	N/A	16,039 (95.8%)
Comorbidity Scores								
CCI (180 days)-ICD9 and ICD10 v2								
...mean (sd)	2.63 (1.40)	2.62 (1.35)	0.01	2.81 (1.57)	2.78 (1.56)	0.02	1.33 (1.37)	1.33 (1.39)
...median [IQR]	2.00 [2.00, 3.00]	2.00 [2.00, 3.00]	0.00	2.00 [2.00, 4.00]	2.00 [2.00, 4.00]	0.00	1.00 [0.00, 2.00]	1.00 [0.00, 2.00]
Non-Frailty; n (%)	1,525 (54.7%)	1,532 (54.9%)	0.00	6,845 (49.0%)	6,801 (48.7%)	0.01	669 (3.0%)	465 (2.1%)
Frailty Score (mean): Empirical Version 365 days, v2								
...mean (sd)	0.17 (0.04)	0.17 (0.04)	0.00	0.17 (0.05)	0.17 (0.05)	0.00	10.70 (9.15)	10.66 (9.45)
...median [IQR]	0.16 [0.14, 0.19]	0.16 [0.14, 0.19]	0.00	0.17 [0.14, 0.20]	0.17 [0.14, 0.20]	0.00	8.94 [4.50, 14.92]	8.82 [4.32, 14.85]
Healthcare Utilization								

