Diabetes: 1 inpatient or 2 outpatient claims within 18	780 (28.0%)	749 (26.8%)	0.03	3,371 (24.1%)	3,331 (23.9%)	0.00	5,636 (25.3%)	5,630 (25.2%)	0.00	9,787 (25.0%)	9,710 (24.9%)	0.00
Intracranial or retroperitoneal hemorrhage: 1 inpatient												
...mean (sd)	0 (0.0%)	1 (0.0%)	#DIV/0!	9 (0.1%)	8 (0.1%)	0.00	20 (0.1%)	17 (0.1%)	0.00	29 (0.1%)	26 (0.1%)	0.00
Peptic Ulcer Disease; n (%)	203 (7.3%)	208 (7.5%)	-0.01	901 (6.5%)	844 (6.0%)	0.02	1,652 (7.4%)	1,633 (7.3%)	0.00	2,756 (7.1%)	2,685 (6.9%)	0.01
Upper GI bleed; n (%)	0 (0.0%)	0 (0.0%)	#DIV/0!	5 (0.0%)	4 (0.0%)	#DIV/0!	0 (0.0%)	**	#VALUE!	5 (0.0%)	#VALUE!	#VALUE!
Lower/ unspecified GI bleed; n (%)	21 (0.8%)	24 (0.9%)	-0.01	104 (0.7%)	98 (0.7%)	0.00	116 (0.5%)	132 (0.6%)	-0.01	241 (0.6%)	254 (0.7%)	-0.01
Urogenital bleed; n (%)	91 (3.3%)	85 (3.0%)	0.02	441 (3.2%)	429 (3.1%)	0.01	671 (3.0%)	628 (2.8%)	0.01	1,203 (3.1%)	1,142 (2.9%)	0.01
Other bleeds; n (%)	29 (1.0%)	27 (1.0%)	0.00	167 (1.2%)	157 (1.1%)	0.01	229 (1.0%)	243 (1.1%)	-0.01	427 (1.1%)	425 (1.1%)	0.00
Prior cancer; n (%)	285 (10.2%)	289 (10.4%)	-0.01	1,288 (9.2%)	1,288 (9.2%)	0.00	2,427 (10.9%)	2,334 (10.5%)	0.01	4,000 (10.2%)	3,911 (10.0%)	0.01
Aspirin; n (%)	13 (0.5%)	11 (0.4%)	0.01	164 (1.2%)	161 (1.2%)	0.00	105 (0.5%)	97 (0.4%)	0.01	282 (0.7%)	269 (0.7%)	0.00
Aspirin/dipyridamole; n (%)	9 (0.3%)	9 (0.3%)	0.00	79 (0.6%)	71 (0.5%)	0.01	90 (0.4%)	84 (0.4%)	0.00	178 (0.5%)	164 (0.4%)	0.01
Other antiplatelet agents; n (%)	17 (0.6%)	13 (0.5%)	0.01	68 (0.5%)	77 (0.6%)	-0.01	134 (0.6%)	125 (0.6%)	0.00	219 (0.6%)	215 (0.6%)	0.00
PGP inhibitors; n (%)	1,098 (39.4%)	1,087 (39.0%)	0.01	6,825 (48.9%)	6,727 (48.2%)	0.01	9,742 (43.6%)	9,629 (43.1%)	0.01	17,665 (45.2%)	17,443 (44.6%)	0.01
Other gastroprotective agents; n (%)	19 (0.7%)	16 (0.6%)	0.01	131 (0.9%)	125 (0.9%)	0.00	165 (0.7%)	156 (0.7%)	0.00	315 (0.8%)	297 (0.8%)	0.00
Number of lipid tests ordered												
...mean (sd)	0.67 (0.86)	0.68 (0.84)	-0.01	0.25 (0.70)	0.24 (0.63)	0.02	0.71 (0.86)	0.71 (0.81)	0.00	0.54 (0.81)	0.54 (0.75)	0.00
...median [IQR]	0.00 [0.00, 1.00]	1.00 [0.00, 1.00]	-1.18	0.00 [0.00, 0.00]	0.00 [0.00, 0.00]	0.00	1.00 [0.00, 1.00]	1.00 [0.00, 1.00]	0.00	0.36 (0.87)	0.43 (0.81)	0.00
Proton pump inhibitor; n (%)	470 (16.8%)	440 (15.8%)	0.03	2,736 (19.6%)	2,724 (19.5%)	0.00	4,221 (18.9%)	4,253 (19.1%)	-0.01	7,427 (19.0%)	7,417 (19.0%)	0.00

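### Trial exclusion 3j (recent malignancy or radiation with poor expected survival) is marked N/A, although a claims proxy is feasible; some excluded-type cancer patients probably remain, with a small likely effect

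*Combined protocol and SAP*

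**What the plan says.** Section 5.2.2 states that eligibility follows the trial as nearly as it can. Appendix A then sets each trial criterion beside its claims implementation.

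- **Criterion 3j**, listed among conditions that raise bleeding risk, reads "Recent malignancy or radiation therapy (≤6 m) and not expected to survive 3 y". Its implementation cell is N/A, and section 5.3 has no corresponding step.
- **Criterion 14** is implemented partly as "CCI >=10 (life expectancy less than the expected duration of the trial", measured over 180 days. Its flowchart row is "Excluded based on Exclusion 14 - CCI (180 days".
- **Criterion 11** excludes coded anemia and thrombocytopenia over 180 days; its label mentions neoplastic and chemotherapy anemia.
- **Appendix B, PS-matched table**, carries a yes/no row, "Prior cancer; n", with 4,000 warfarin (10.2%) and 3,911 dabigatran patients (10.0%). The row states no look-back, stage or treatment.
- **Section 9** sets the adjustment: "The PS should include the complete list of covariates (excluding laboratory values, which are missing in some patients". The covariate list also holds two graded general measures, "CCI (180 days)-ICD9 and ICD10 v2" and "Frailty Score (mean): Empirical Version 365 days, v2".

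**The concern.** The study is judged against the trial's result, so a trial exclusion left unapplied lets in patients to whom that result does not extend. Criterion 3j is a bleeding-risk exclusion, and major bleeding is the control outcome used to judge validity (sections 1.4 and 6.3.1, trial RR 0.93). Advanced cancer can plausibly affect stroke, bleeding and death, as well as the choice of anticoagulant. A balanced yes/no cancer row cannot show whether metastatic or actively treated disease is balanced within it.

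N/A also sits oddly with the plan's practice elsewhere in Appendix A. An ejection fraction below 40% becomes systolic heart-failure codes (2b), very high blood pressure becomes malignant-hypertension or hypertensive-crisis codes (3i), and short life expectancy becomes a CCI cut-off (14). A coded proxy for 3j would be of the same kind.

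**Working it through.** **1. How many matched patients carry the cancer flag** (Appendix B, PS-matched table)

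- Warfarin: 285 + 1,288 + 2,427 = 4,000; 4,000 / 39,070 = 10.24%.
- Dabigatran: 289 + 1,288 + 2,334 = 3,911; 3,911 / 39,070 = 10.01%.
- Combined: 7,911 / 78,140 = 10.12%.
- Standardized difference: (p - q) / sqrt([p(1 - p) + q(1 - q)] / 2) = 0.008, in line with the tabulated 0.01.

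**2. What the CCI rule removed** (section 5.3, patients removed over patients entering that step)

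| Database | Removed / entering | Share | Matched patients (section 10) |
|---|---|---|---|
| Optum | 7 / 25,623 | 0.03% | 5,580 |
| MarketScan | 47 / 82,843 | 0.06% | 27,920 |
| Medicare | 1,939 / 163,475 | 1.19% | 44,640 |
| All | 1,993 / 271,941 | 0.73% | 78,140 |

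Optum and MarketScan, where the rule removes almost nobody, supply 33,500 / 78,140 = 43% of matched patients.

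**3. General scores after matching** (Appendix B, warfarin against dabigatran)

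- CCI mean: Optum 2.63 and 2.62; MarketScan 2.81 and 2.78; Medicare 1.33 and 1.33.
- Frailty mean: Optum 0.17 and 0.17; MarketScan 0.17 and 0.17; Medicare 10.70 and 10.66.

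Overall illness burden is balanced. These scores do not show cancer stage or treatment.

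**4. Possible bias (illustration; advanced-cancer shares and risk are assumed)**

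Let a be the share of prior-cancer patients with advanced disease and RR their relative outcome risk. The hazard ratio is then multiplied by approximately

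(1 + 0.1001 × a_dabigatran × (RR - 1)) / (1 + 0.1024 × a_warfarin × (RR - 1)).

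- a = 10% in both arms, RR 1.5 to 3: factor 0.9999 to 0.9996, effectively none.
- a = 20% warfarin and 10% dabigatran, RR 1.5: 1.0050 / 1.0102 = 0.995; 0.66 becomes 0.657.
- Same split, RR 3: 1.0200 / 1.0410 = 0.980; 0.66 becomes 0.647.
- A more extreme split, 30% and 15%, RR 3: 0.970.

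The direction is assumed too; an imbalance the other way would reverse the sign.

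**5. Cost in power**

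Events = N × 5.64 / 1,000. Power = Φ(|ln HR| × sqrt(events / 4) - 1.96), with HR 0.66 for superiority, and the margin 1.46 with a true HR of 1 for non-inferiority. This reproduces section 10: 440.71 events give Φ(0.4155 × 10.497 - 1.96) = 0.992 and Φ(0.3784 × 10.497 - 1.96) = 0.978.

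Assume a share f of the 7,911 is removed and the risk is unchanged:

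| f | N | Events | Superiority | Non-inferiority |
|---|---|---|---|---|
| 5% | 77,744 | 438 | 0.992 | 0.977 |
| 25% | 76,162 | 430 | 0.991 | 0.975 |
| 100% | 70,229 | 396 | 0.985 | 0.965 |

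**The case against.** The best defense has four parts.

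**Prognosis is not in claims.** Criterion 3j needs recent disease or radiation and also a survival judgement, and other intent- or judgement-based criteria (3b, 3g, 4, 6) are N/A as well. Appendix A has a color-coding column that may explain the choice, but the colors are not visible in the text reviewed, so the absence of a reason cannot be held against the plan. What stands is that any proxy is approximate. In particular, excluding everyone with a chemotherapy or radiation encounter would drop the survival condition and remove patients with curable disease whom the trial allowed.

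**Adjustment goes beyond the flag.** A reader might infer that a yes/no row is the only protection against confounding by cancer severity. The documents do not support that: the propensity score also takes the CCI, the frailty score and other markers of illness. Some Appendix B rows are cut off in the text reviewed, so the safe statement is that prior cancer is the only cancer-specific diagnosis row shown.

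**Other exclusions already act.** A reader might infer from Optum and MarketScan that advanced-cancer patients simply stay in. The CCI rule removed 1,939 patients in Medicare, and it is the last step, after the anemia, coagulation, liver and surgery exclusions. Low counts there do not prove that advanced cancer remains. Still, none of these rules targets cancer, and criterion 14 concerns survival over the trial's duration rather than 3 years.

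**The effect is small and unobserved.** A reader might take 10.1% as the number wrongly included, or a bias figure as an estimate. Neither holds: the flag is any prior cancer over an unstated window, and no within-cancer imbalance is reported. The excess of deaths as a censoring reason on warfarin (369 against 288, section 9) is not evidence of one either, since it is not cancer-specific and may partly be a drug effect.

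**Conclusion.** The concern holds as a modest point about fidelity to the trial and residual confounding. Criterion 3j is unapplied although cancer is coded and comparable criteria receive proxies. The CCI and anemia rules replace it only in part, so some patients whom the trial excluded probably remain. How many is unknown. Bias on the hazard ratio is probably small, about 0 to -2% under the main assumed inputs (advanced disease in 10% to 20% of flagged patients, at most a twofold imbalance, relative risk 1.5 to 3), and close to zero without imbalance within the cancer group. Set against a trial estimate of 0.66 (0.53 to 0.82), this does not threaten the study; the case for acting is that the remedy is cheap and brings both the stroke and the bleeding comparison closer to the trial.

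**What to change.** 1. Map 3j to secondary or metastatic malignancy codes in days -180 to 0 as an exclusion, and add the step to the section 5.3 flowchart. Note that it is a proxy for the survival condition.
2. Report the number removed by arm and by database, so that the size of the issue becomes known.
3. Run the wider filters as sensitivity analyses only, because they go beyond 3j: any chemotherapy or radiation encounter in the 180 days, and any prior cancer.
4. State the look-back of the prior-cancer row.

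The cost is one more code list, a re-run of the match with its balance and power tables, and a slightly smaller cohort. The bound is the last row of the power table: 396 expected events, with pooled power of 98.5% for superiority and 96.5% for non-inferiority. The metastatic-code exclusion alone should cost much less.
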